#### 11.1.5 Duration of Response

**Duration of overall response:** The duration of overall response is measured from the time measurement criteria are met for CR or PR (whichever is first recorded) until the first date that recurrent or progressive disease is objectively documented (taking as reference for progressive disease the smallest measurements recorded since the treatment started).

The duration of overall CR is measured from the time measurement criteria are first met for CR until the first date that progressive disease is objectively documented.

**Duration of stable disease:** Stable disease is measured from the start of the treatment until the criteria for progression are met, taking as reference the smallest measurements recorded since the treatment started, including the baseline measurements.

### 11.1.6 Progression-Free Survival (PFS)

PFS is defined as the duration of time from start of treatment to time of progression or death, whichever occurs first.

### 11.1.7 Response Review

There is no independent or central review of the radiology assessments planned for this trial. It is the responsibility of each Principal Investigator to ensure that tumor assessments are reported per the RECIST 1.1 criteria outlined above.

## 12. STATISTICAL CONSIDERATIONS

### 12.1 Study Design/Endpoints

This is an open label, phase II clinical trial of nivolumab and ipilimumab in subjects with advanced, well-differentiated nonfunctional NET of the pancreas, lung or gastrointestinal (GI) tract. The primary endpoint is ORR defined as RECIST 1.1 partial response (PR) or complete response (CR).

Simon two-stage design (28) was used to evaluate the primary endpoint, with details as described in section 12.2.

### 12.2 Sample Size/Accrual Rate

The optimal two-stage design to test the null hypothesis that  $P \leq 0.050$  versus the alternative that  $P \geq 0.150$  has an expected sample size of 29.51 and a probability of early termination of 0.736. If the regimen is actually not effective, there is a 0.097 probability of concluding that it is (the target for this value was 0.100). If the regimen is actually effective, there is a 0.199 probability of concluding that it is not (the target for this value was 0.200). After testing the drug on 20 patients in the first stage, the trial will be terminated if 1 or fewer respond. If the trial goes on to the second stage, a total of 56 patients will be studied. If the total number responding is less than or equal to 4, the regimen is rejected.

Assuming a 15% screening failure rate, it is estimated that approximately 64 subjects will be enrolled in order to achieve 56 treated subjects.

### 12.3 Analysis and Summary of Endpoints

#### 12.3.1 Primary Endpoints

The primary endpoint is ORR (per RECIST v1.1 criteria) among all treated subjects. All treated subjects is defined as all subjects who received at least one complete dose of nivolumab and ipilimumab. ORR is defined as the number of subjects with a best overall response (BOR) of confirmed CR or PR, divided by the number of treated subjects.

BOR is defined as the best response designation, recorded between baseline and the date of objectively documented progression per RECIST 1.1 or the date of initiation of palliative local therapy or the date of initiation of subsequent anticancer therapy,

whichever occurs first. For subjects without documented progression or palliative local therapy or subsequent anti-cancer therapy, all available response designations will contribute to the BOR determination. For subjects who continue treatment beyond progression, the BOR will be determined based on response designations recorded up to the time of the initial RECIST 1.1-defined progression.

Complete or partial responses may be claimed only if the criteria for each are met at a subsequent time point of  $\geq 4$  weeks later.

Further characterization of the response will include time to objective response (time from first dosing date to first CR or PR) and depth of response (maximum tumor shrinkage in target lesions).

The analysis of the primary endpoint ORR will be performed six months after the last subject's first treatment.

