#### 4.1.3 Dosing

Nivolumab and ipilimumab will be administered on the same day. Separate infusion bags and filters must be used for each infusion. Nivolumab is to be administered first. The second infusion will always be ipilimumab and will start no sooner than 30 minutes after completion of the nivolumab infusion. Subjects who require small volumes may infuse over < 60 minutes but no less than 20 minutes.

Nivolumab and ipilimumab may be diluted in 0.9% Sodium Chloride Solution or 5% Dextrose solution.

Dosing calculations for ipilimumab should be based on the body weight. If the subject's weight on the day of dosing differs by > 10% from the weight used to calculate the prior dose, the dose must be recalculated. All doses should be rounded to the nearest milligram. There will be no dose modifications allowed.

Subjects may be dosed with nivolumab no less than 12 days from the previous dose. There are no premedications recommended.

Doses of nivolumab and/or ipilimumab may be interrupted, delayed, or discontinued depending on how well the subject tolerates the treatment. For more details, see **Section 5.2** (dose delays).

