#### **5.5 Management of Nivolumab or Ipilimumab Infusion Reactions**

Since nivolumab and ipilimumab contain only human immunoglobulin protein sequences, they are unlikely to be immunogenic and induce infusion or hypersensitivity reactions. However, if such a reaction were to occur, it might manifest with fever, chills, rigors, headache, rash, pruritus, arthralgias, hypo- or hypertension, bronchospasm, or other symptoms. All Grade 3 or 4 infusion reactions should be reported within 24 hours to the IND Sponsor and reported as an SAE if criteria are met. Infusion reactions should be graded according to NCI CTCAE (Version 4.0) guidelines.

Treatment recommendations are provided below and may be modified based on local treatment standards and guidelines, as appropriate:

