##### **5.5.2 For Grade 2 symptoms: (moderate reaction requires therapy or infusion interruption but responds promptly to symptomatic treatment [e.g., antihistamines, non-steroidal anti-inflammatory drugs, narcotics, corticosteroids, bronchodilators, IV fluids]; prophylactic medications indicated for $\geq$ 24 hours)**

Stop the nivolumab or ipilimumab infusion, begin an IV infusion of normal saline,

and treat the subject with diphenhydramine 50 mg IV (or equivalent) and/or acetaminophen/paracetamol 325 to 1000 mg; remain at bedside and monitor subject until resolution of symptoms. Corticosteroid and/or bronchodilator therapy may also be administered as appropriate. If the infusion is interrupted, then restart the infusion at 50% of the original infusion rate when symptoms resolve; if no further complications ensue after 30 minutes, the rate may be increased to 100% of the original infusion rate. Monitor subject closely. If symptoms recur, then no further nivolumab or ipilimumab will be administered at that visit. Administer diphenhydramine 50 mg IV, and remain at bedside and monitor the subject until resolution of symptoms. The amount of study drug infused must be recorded on the electronic case report form (eCRF).

For future infusions, the following prophylactic premedications are recommended: diphenhydramine 50 mg (or equivalent) and/or acetaminophen 325 to 1000 mg should be administered at least 30 minutes before nivolumab or ipilimumab infusions. If necessary, corticosteroids (up to 25 mg of SoluCortef or equivalent) may be used.

5.5.3 For Grade 3 or 4 symptoms: (severe reaction, Grade 3: prolonged [i.e., not rapidly responsive to symptomatic medication and/or brief interruption of infusion]; recurrence of symptoms following initial improvement; hospitalization indicated for other clinical sequelae [e.g., renal impairment, pulmonary infiltrates]. Grade 4: Life threatening; pressor or ventilatory support indicated)

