Immediately discontinue infusion of nivolumab or ipilimumab. Begin an IV infusion of normal saline and treat the subject as follows: Recommend bronchodilators, epinephrine 0.2 to 1 mg of a 1:1000 solution for subcutaneous administration or 0.1 to 0.25 mg of a 1:10,000 solution injected slowly for IV administration, and/or diphenhydramine 50 mg IV with methylprednisolone 100 mg IV (or equivalent), as needed. Subject should be monitored until the investigator is comfortable that the symptoms will not recur. Nivolumab or ipilimumab will be permanently discontinued. Investigators should follow their institutional guidelines for the treatment of anaphylaxis. Remain at bedside and monitor subject until recovery of the symptoms.

In case of late-occurring hypersensitivity symptoms (e.g., appearance of a localized or generalized pruritus within 1 week after treatment), symptomatic treatment may be given (e.g., oral antihistamine or corticosteroids).

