## 6. ADVERSE EVENTS: LIST AND REPORTING REQUIREMENTS

This study will use the descriptions and grading scales found in the revised National Cancer Institute Common Terminology Criteria for Adverse Events (CTCAE) Version 4.0 for adverse event reporting that can be found at [http://ctep.cancer.gov/protocolDevelopment/electronic\\_applications/ctc.htm](http://ctep.cancer.gov/protocolDevelopment/electronic_applications/ctc.htm).

Information about all AEs, whether volunteered by the subject, discovered by investigator questioning, or detected through physical examination, laboratory test or other means, will be collected, recorded, and followed as appropriate.

All AEs and SAEs experienced by subjects will be collected and reported from the first dose of nivolumab, throughout the study, and will only be followed for 4 weeks unless related to the investigational agent. All SAEs will be collected for 100 days after the last dose of nivolumab. Subjects who have an ongoing AE related to the study procedures and/or medication(s) may continue to be periodically contacted by a member of the study staff until the event is resolved or determined to be irreversible by the investigator.

**Laboratory abnormalities:** Laboratory abnormalities present at the screening visit will be recorded as pre-treatment signs and symptoms. After study treatment administration, all grade 3 and 4 clinical laboratory results that represent an increase in severity from baseline will be reported as adverse events. A grade 1 or 2 clinical laboratory abnormality should be

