### 12.4.2 Methods for Secondary Endpoints

Secondary endpoints will be evaluated based on the treated population.

Time to event distribution will be estimated using Kaplan Meier techniques. This will be done for PFS. Median PFS along with 95% CI will be constructed based on a log-log transformed CI for the survivor function. Rates at fixed time points (e.g., PFS at 6 and 12 months) will be derived from the Kaplan Meier estimate and corresponding confidence interval will be derived based on Greenwood formula for variance derivation and on log-log transformation applied on the survivor function.

The DCR will be summarized for subjects who achieve confirmed PR or CR using the Kaplan-Meier (KM) product-limit method. Median values of DCR, along with

95% CI will be constructed based on a log-log transformed CI for the survivor function.

The DOR will be summarized for subjects who achieve confirmed PR or CR using the Kaplan-Meier (KM) product-limit method. Median values of DOR, along with 95% CI will be constructed based on a log-log transformed CI for the survivor function.

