#### 12.4.3 Safety Analyses

Safety analysis will be performed in all treated subjects. Descriptive statistics of safety will be presented using National Cancer Institute (NCI) Common Terminology Criteria for Adverse Events (CTCAE) version 4.0. All on-study AEs, drug-related AEs, SAEs and drug-related SAEs, AEs and drug-related AEs leading to drug discontinuation will be tabulated using worst grade per NCI CTCAE v 4.0 criteria by system organ class and preferred term, based on MedDRA terminology. On-study lab parameters including hematology, coagulation, chemistry, liver function and renal function will be summarized using worst grade per NCI CTCAE v 4.0 criteria.

Frequency, management and resolution of IMAEs will be analyzed. A tabular summary of the incidence of overall IMAEs (by preferred term) and serious IMAEs will be performed. A descriptive analysis of IMAEs including time-to-onset, severity, duration, action taken with the study drug, dosing delays of the study drug, corticosteroid details, re-challenge information and outcome of the AE will be individually characterized by IMAE category ([Section 6.6.1](#)).

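### Safety tables are restricted to subjects with a complete dose of both drugs, so an exposed subject whose first infusion is stopped for a severe reaction is left out as the plan is written

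*Combined protocol and SAP*

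**What the plan says.** Section 12.3.1 sets the population for the primary endpoint: "All treated subjects is defined as all subjects who received at least one complete dose of nivolumab and ipilimumab". Two later sections reuse it. Section 12.4.3 says "Safety analysis will be performed in all treated subjects". Section 12.4.2 says "Secondary endpoints will be evaluated based on the treated population", and 12.3.2 lists safety and tolerability among those endpoints. The supplied text defines no separate safety set.

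The dosing rules matter here. Section 4.1.3 gives nivolumab first and then states: "The second infusion will always be ipilimumab and will start no sooner than 30 minutes after completion of the nivolumab infusion". For Grade 3-4 infusion reactions, section 5.5.3 has the infusion stopped at once and adds: "Nivolumab or ipilimumab will be permanently discontinued".

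Data collection carries no completeness condition. Section 6 says "All AEs and SAEs experienced by subjects will be collected and reported from the first dose of nivolumab", and section 5.5 says "All Grade 3 or 4 infusion reactions should be reported within 24 hours to the IND Sponsor".

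**The concern.** Entry to the safety set depends on a safety outcome. A subject who reacts severely during the first infusion of a drug never receives a complete dose of it, and so does not meet the definition. The exclusion removes that subject from the denominator and the severe event from the numerator together.

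The tables affected are those 12.4.3 promises: AEs, SAEs and AEs leading to discontinuation. Safety and tolerability is a secondary objective (1.2.1). In a single-arm trial with 20 or 56 treated subjects, a table showing no severe infusion reaction and one showing a single reaction are different statements about the regimen.

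**Working it through.** **1. Does the text exclude the subject?**
- First nivolumab infusion stopped for a Grade 3-4 reaction: nivolumab is permanently discontinued (5.5.3), so there is never a complete nivolumab dose. Not in the set.
- First nivolumab complete, first ipilimumab stopped for a Grade 3-4 reaction: never a complete ipilimumab dose. Not in the set.
- First nivolumab complete, ipilimumab never given for any reason: not in the set.
- One drug continued alone (5.2.5): membership is not restored, because the definition joins the drugs with *and*.
- Reaction that starts after both first infusions are complete, or on a later cycle: in the set and counted.
- Grade 2 interruption (5.5.2): need not exclude, because the infusion may be restarted or a complete dose given later.

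**2. The plan's own design figures (12.2).** With 1/20 and 4/56 as the rejection limits and p = 0.05:
- Probability of early termination = 0.95^20 + 20 × 0.05 × 0.95^19 = 0.736.
- Expected N = 20 + 36 × (1 − 0.7358) = 29.51.
- Exact enumeration gives type I error 0.097, and type II error 0.199 at p = 0.15.

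All four agree with 12.2. None of them depends on which subjects enter the safety tables.

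**3. How likely is at least one exclusion?** The documents give no rate, so the per-subject rate r is an assumption. The chance that at least one exposed subject is excluded before n treated subjects have been accrued is 1 − (1 − r)^n.

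| Assumed r | n = 56 | n = 20 (stage 1 only) |
|---|---|---|
| 0.1% | 5% | 2% |
| 0.5% | 24% | 10% |
| 1% | 43% | 18% |
| 2% | 68% | 33% |

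**4. What would one case do to the table?** Section 12.2 accrues to 56 treated subjects, so under the definition an excluded subject is replaced and 57 are exposed. Suppose one excluded case and no other severe infusion reaction (Clopper-Pearson 95% limits; for zero events the upper limit is 1 − 0.025^(1/n)).
- Full trial, plan as written: 0/56 = 0% (0 to 6.4%).
- Full trial, any exposure: 1/57 = 1.8% (0.04 to 9.4%).
- Stop after stage 1, plan as written: 0/20 = 0% (0 to 16.8%).
- Stop after stage 1, any exposure: 1/21 = 4.8% (0.1 to 23.8%).

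The stage 1 figures assume that the 20 in stage 1 are also counted in treated subjects.

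**The case against.** The best reply is that the wording is loose rather than restrictive. *Complete dose* is undefined, 12.2 contrasts treated subjects only with screening failures, and 12.4.3 promises all on-study AEs. A team could in good faith tabulate an exposed subject. This stands in part: omission is not certain. But the text names a complete dose of both drugs and provides no route back in. Section 4.3 treats doses within 10% of the calculated dose as full. That rule concerns pharmacy adjustment and at most covers a nearly finished infusion. Reading *and* as *or* would still lose a subject stopped during the first nivolumab infusion, unless a complete ipilimumab dose followed.

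The second reply is that the case is rare and drives no decision. Rarity stands: 5.5 calls such reactions unlikely, no exclusion is the likelier outcome at assumed rates up to 1%, and after a stage 1 stop it is likelier at every rate shown. The two intervals for the full trial overlap heavily. The safety analysis is descriptive, and no toxicity stopping boundary is computed on this set.

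A reader might infer that participants are less protected. The documents do not support that: AEs are collected from the first nivolumab dose, Grade 3-4 infusion reactions go to the IND Sponsor within 24 hours, and the DSMB reviews toxicity at least annually (10.1). A reader might also infer that all severe infusion reactions disappear from the tables. They do not; only those that prevent a complete first dose of one drug are lost.

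**Conclusion.** The point holds as a defect in a stated rule. As written, the safety set excludes some exposed subjects because of a safety outcome, and the tabulated rate of severe infusion reactions can be biased down. The harm is confined to the reported safety summary.

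The likely size is small: one case changes 1/57 to 0/56, or 1/21 to 0/20 after a stage 1 stop. The frequency is unknown, and the 5% to 68% range for a full trial rests entirely on assumed rates of 0.1% to 2%. Those rates stand for either route out of the set: a stopped first infusion, or ipilimumab never given. The severe-reaction comparison applies to the first route.

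It should not be read as a finding against the ORR denominator or the two-stage design, which reproduces as stated.

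**What to change.** - Define a safety set of all subjects who received any amount of nivolumab or ipilimumab.
- Use it for every table in 12.4.3 and for the safety endpoints in 12.3.2.
- Amend 12.4.2 so that the treated population applies to the efficacy secondary endpoints only. Otherwise 12.4.2 would still place safety, a secondary endpoint, on the complete-dose set and contradict the amended 12.4.3.
- Leave the ORR denominator in 12.3.1, the design in 12.2 and the infusion-reaction rules in 5.5 as they are.

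The cost is wording. No new data are needed, because section 6 already collects AEs from the first nivolumab dose. The amount infused is not needed for an any-exposure set; the instruction to record it on the case report form appears only under Grade 2 reactions (5.5.2), so the fix should not rely on it. Sample size, power and type I error do not change. The one small downside is that the reported rate of severe reactions may be slightly higher. The change should be made before the analysis, so that results cannot influence it.

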#### 4.11 Duration of Study

The analysis of the primary endpoint ORR will be performed six months after the last subject's first treatment. Additional survival follow-up may continue for up to 5 years from the primary analysis. The study will end once survival follow-up has concluded.

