	
a: LDH, AST, ALT, ALP, T. bili, BUN or serum urea level, creatinine, albumin, Ca, Mg, Na, K, Cl, phosphate, glucose, amylase, lipase, TSH, Free T4, Free T3, within 14 days prior to first dose.
 
b: Hep B/C (HBV sAg, HCV antibody or HCV RNA), within 28 days prior to first dose.
 
c: Thyroid Function Testing to be evaluated every 6 weeks
 
d: A serum or urine pregnancy testing is required prior to study enrollment/registration, also within 24 hours prior to D1 (and extension to 72 hours may be granted if unable to obtain within 24 hrs). Must be reassessed every 4 weeks.
 
e: CT scan of the chest and other relevant sites as well as MRI brain with gadolinium (or CT scan brain with contrast if MRI is contraindicated) will be performed <math>\leq</math> 4 weeks prior to the start of therapy. For subsequent scans, may be done within +/- 7 days of intended visit.
 
f: Within 72 hrs prior to dosing to include CBC w/ differential, AST, ALT, ALP, T. bili, BUN or serum urea level, creatinine, albumin, Ca, Mg, Na, K, Cl, LDH, phosphate, glucose, amylase, lipase, TSH (with reflexive Free T4 and Free T3). Note: C1D1 labs do not need to be repeated if they were performed within 14 days of dosing.
 
g: All treatments may be performed +/- 2 days of the intended treatment administration dates schedule for all cycles.
 
h: Recent sample or archival obtained. One (1) formalin-fixed paraffin embedded tumor tissue block or a minimum of 10 unstained tumor tissue sections are acceptable.
 
i: Mandatory fresh tissue will be collected for biomarker studies at baseline and on treatment (week 6-8) for patients enrolled in the second stage of the study.
 
j: Immunogenecity samples should be collected just before the administration of the first drug (preferably within 30 minutes).
 
k: Adverse event evaluation as per Common Terminology Criteria for Adverse Events (CTCAE) version 4.0
 
l: Survival follow-up may be done via phone call for survival status and subsequent therapy
 
m: CT if the subject came off study for reasons other than PD
 
n: EOT assessments do not need to be repeated if performed within 14 days
 
o: In order to minimize the need for research-only in-person visits, telemedicine visits may be substituted for in-person clinical trial visits or portions of clinical trial visits where determined to be appropriate and where determined by the investigator not to increase the participant's risks. Prior to initiating telemedicine for study visits the study team will explain to the participant, what a telemedicine visit entails and confirm that the study participant is in agreement and able to proceed with this method. Telemedicine acknowledgement will be obtained in accordance with the Guidance for Use of Telemedicine in Research. In the event telemedicine is not deemed feasible, the study visit will proceed as an in-person visit. Telemedicine visits will be conducted using HIPAA compliant method approved by the Health System and within licensing restrictions.
								

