# **11. MEASUREMENT OF EFFECT**

## **11.1 Antitumor Effect**

For the purposes of this study, patients should be re-evaluated every 6 weeks. In addition to a baseline scan, confirmatory scans will also be obtained 6 (not less than 4) weeks following initial documentation of an objective response.

Response and progression will be evaluated in this study using the new international criteria proposed by the revised Response Evaluation Criteria in Solid Tumors (RECIST) guideline (version 1.1). Changes in the largest diameter (unidimensional measurement) of the tumor lesions and the shortest diameter in the case of malignant lymph nodes are used in the RECIST criteria.

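### The six-month ORR analysis date falls before a week-24 response can be confirmed in the last-treated subjects; the bias is one-directional but small, and the stage-1 look states no follow-up horizon

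*Combined protocol and SAP*

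**What the plan says.** Sections 4.11 and 12.3.1 give the same analysis date: "The analysis of the primary endpoint ORR will be performed six months after the last" subject's first treatment. Neither mentions responses still awaiting confirmation.

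Section 11.1 sets the scan interval: "For the purposes of this study, patients should be re-evaluated every 6 weeks". A study calendar footnote (section 9) adds a window: "For subsequent scans, may be done within +/- 7 days of intended visit".

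Confirmation is part of the endpoint. Section 12.3.1: "Complete or partial responses may be claimed only if the criteria for each are met at a subsequent time point of" at least 4 weeks later. Section 11.1 plans the timing: "confirmatory scans will also be obtained 6 (not less than 4) weeks following initial documentation of an objective response". The ORR denominator is all treated subjects. For a subject without progression, palliative local therapy or subsequent anticancer therapy, every available assessment counts towards best overall response.

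The stage-1 rule in section 12.2 reads: "After testing the drug on 20 patients in the first stage, the trial will be terminated if 1 or fewer respond". It gives no follow-up per subject and does not say how pending confirmations are handled or whether accrual pauses. The final rule there rejects the regimen at 4 or fewer responders of 56.

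**The concern.** The cut-off date and the confirmation rule do not fit together. For the last subjects treated, the fourth scheduled scan falls before the cut-off but its confirmation falls after it. Because the denominator includes every treated subject, a pending response is counted as a failure. The error can only lower the observed ORR, so it works against an active regimen.

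A threshold of a few responders makes single subjects matter. If a confirmation is pending at the cut-off, the team must decide after the fact whether to wait for it, in an open-label trial without central radiology review (11.1.7). The stage-1 look raises the same question with a threshold of 1 versus 2 responders in 20, and a stop at that point ends the trial.

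**Working it through.** **Reproducing the design (12.2).** Inputs: 20 subjects in stage 1, stop at 1 or fewer; 56 in total, reject the regimen at 4 or fewer; response rates 0.05 and 0.15. Let X1 be the stage-1 responders and X2 those among the further 36.
- P(stop) = P(X1 ≤ 1 | 20, p) = 0.736 at p = 0.05 and 0.176 at p = 0.15.
- P(accept) = Σ over x ≥ 2 of P(X1 = x) × P(X2 ≥ 5 − x | 36, p) = 0.097 at p = 0.05 and 0.801 at p = 0.15.
- Expected sample size at p = 0.05 is 20 + (1 − 0.736) × 36 ≈ 29.5.

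These match the plan's 0.736, 0.097, 0.199 (= 1 − 0.801) and 29.51.

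**Timing in the last-treated subject.**
- Six months = 365.25 / 2 / 7 = 26.1 weeks.
- Scans fall at weeks 6, 12, 18 and 24, each ± 1 week.
- Fourth scan one week early, minimum interval: 23 + 4 = week 27, which is 0.9 weeks too late.
- On time, minimum interval: 24 + 4 = week 28, 1.9 weeks too late.
- On time, planned interval: 24 + 6 = week 30, 3.9 weeks too late.
- The week-18 scan is confirmable at week 22 to 24, so it is the last scheduled scan that can count.

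**Who is affected.** A subject dosed d weeks before the last one has reached week 26.1 + d at the cut-off. The week-24 scan is lost only when d is below about 0.9 to 3.9 weeks (4.9 if that scan is a week late and confirmed 6 weeks later). The documents give no accrual rate. Assuming 1 to 6 subjects per month, the number affected is 1 + rate × (7 × 12 / 365.25) × gap. That is 1 + 1 × 0.230 × 0.9 = 1.2 at the low end and 1 + 6 × 0.230 × 3.9 = 6.4 at the high end, so about 1 to 6.

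**Effect on final power (12.2 rule, p = 0.15).** Stage 1 is left intact. The last k stage-2 subjects respond with probability 0.15 × (1 − f), where f is the assumed share of responses first seen at week 24.

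| k | f = 10% | f = 30% | all lost |
|---|---|---|---|
| 1 | 0.801 | 0.800 | 0.798 |
| 3 | 0.800 | 0.798 | 0.791 |
| 5 | 0.799 | 0.796 | 0.782 |
| 6 | 0.799 | 0.795 | 0.777 |

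**Stage 1, conditional.** If only a share g of eventual responders is confirmed at the look and the final count is complete, P(stop) = P(X ≤ 1 | 20, 0.15g):
- g = 100%: P(stop) 0.176, power 0.801
- g = 90%: P(stop) 0.227, power 0.753
- g = 80%: P(stop) 0.289, power 0.694

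The shares g are assumptions; the documents give no response timing.

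**The case against.** The strongest reply is that the final-analysis effect is confined to a handful of subjects. This stands. A reader might infer that late responses are scored as non-responses throughout the trial, or might apply a percentage loss to all 56 subjects. The documents do not support that: all available assessments count, so anyone dosed more than about 4 to 5 weeks before the last subject has passed the confirmation date for the week-24 scan. A final cut-off also cannot cause extra stopping at stage 1. Any fixed cut-off leaves some first responses pending, so the exact date is partly a design preference.

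A reader might also take section 5.3 as evidence that slow responses are expected. That section concerns benefit after initial progression, and 12.3.1 excludes post-progression assessments from best overall response, so it lends no support.

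It is tempting to say that one pending scan reverses the primary decision at 5 versus 4 responders. That holds only under 12.2. Section 12.4.1 instead requires the lower 95% confidence bound to exceed 15%, which at n = 56 needs 15 responders (14 gives 14.4%, 15 gives 15.8%). The two rules conflict.

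On stage 1, a reader might conclude that the plan stops before the 20 subjects are assessed. The wording can equally mean after evaluation, and responding naturally carries the confirmed definition in 12.3.1. The Data Safety Monitoring Board review (10.1, at least annually) and the monthly meetings (10.2) neither set a horizon nor imply a premature stop. What remains is that the follow-up is not stated.

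**Conclusion.** The analysis date and the confirmation requirement are inconsistent for the last-treated subjects, even with the scan window used in full. The bias is one-directional and small: power falls by about 0.6 points or less (0.801 to 0.795) under the assumed 1 to 6 affected subjects and 10 to 30% of responses first seen at week 24, and by about 2.4 points (to 0.777) if every response in the last 6 is lost. These figures apply to the 12.2 rule only.

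The stage-1 part is missing detail, not a demonstrated early stop. It still merits a sentence, because the stated 0.199 holds only with complete ascertainment at that look, and the conditional loss there is larger (power 0.753 or 0.694 at 90% or 80% confirmed).

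**What to change.** **Sections 4.11 and 12.3.1.** Keep six months after the last subject's first dose as the last date for a first response, and include the already scheduled confirmatory scans for responses pending on that date. Confirmation takes 4 to 6 weeks, so the primary analysis moves by about that much. Alternatively, set the cut-off at 31 weeks (24 + 6 + 1) or 32 weeks (24 + 1 + 6 + 1), which is about 5 to 6 weeks later than 26.1. The first option is cleaner because it leaves no first response within the window unresolved.

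**Section 12.2.** Apply the same horizon to stage 1. Stop only when all 20 subjects have reached it, or have progressed, died or withdrawn, with 1 or fewer confirmed responses. Continue as soon as a second response is confirmed. State whether accrual is held meanwhile; the cost is a possible accrual pause after subject 20.

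**Sections 12.2 and 12.4.1.** Reconcile the two final decision rules, since the consequence of one pending response depends on which applies.

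The text changes amount to a few sentences, and with complete ascertainment the 12.2 design keeps its stated error rates.
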